2.1. Background

Schizophrenia is a complex psychiatric disorder comprising several clinical features. While the most well-known schizophrenia symptom domains are the so-called positive symptoms, e.g., hallucinations, delusions, disorganization of thought, bizarre behavior, and incongruity of affect, schizophrenics also commonly experience so-called negative symptoms, e.g., avolition (loss of motivation), blunt affect, alogia (reduced speech), and anhedonia (reduced ability to experience pleasure), mood disorders, and cognitive impairment. Cognitive impairment associated with schizophrenia (CIAS) is observed in most cases, usually precedes psychosis, and can involve deficits in a broad range of cognitive domains. Cognitive impairment is considered a core feature of schizophrenia and represents an area of significant unmet medical need.

Cognitive deficits in schizophrenia include problems in speed of processing, attention/vigilance, working memory, verbal learning, visual learning, reasoning and problem solving, and social cognition [1]. These cognitive deficits are believed to underlie much of the significant functional impairments observed in schizophrenia, such as impairment in independent living skills, social functions, vocational functioning, and self-care [2]. Thus, the core nature of CIAS and the associations that have been demonstrated with functional disability suggest that improving cognitive impairment may lead to improved functional outcomes [3]. The cognitive impairments manifest as deficits not only in high-level processes, such as working memory or executive processing, but also as deficits in neurophysiological responses to simple auditory and visual stimuli [4].

Mismatch negativity (MMN) is an established biomarker of cerebral cortical function [5]. This signal is obtained as an evoked potential during an auditory oddball task in which a subject is repeatedly exposed to auditory tones and a small proportion of those tones (the “deviant” stimuli) differ from the others (the “standard” stimuli) in their pitch frequency or duration. Typically, the tones are presented and the evoked potentials are recorded while subjects are engaged on a different task, such as reading. Normally, the occurrence of a deviant stimulus increases the amplitude of the negative component in the evoked potential occurring at around 200 msec. MMN is the difference in amplitude between deviant and standard stimuli responses and is considered to represent an aspect of pre-attentive novelty detection. MMN is consistently reduced in schizophrenia patients relative to healthy individuals, a finding extensively replicated

and with a large effect size (Cohen's $d = 1$), and this reduction (impairment) in MMN is associated with poor psychosocial functioning. Thus, MMN is potentially a useful biomarker in studies seeking to establish whether candidate therapeutic compounds may have a beneficial effect on CIAS.

2.2. Clinical

Two human clinical studies of CVN058 have been completed (ENV8058_101 and TAK-058-1002).

CVN058 is orally absorbed and readily passes the blood brain barrier, allowing it to occupy cortical 5-HT3 receptors. In study ENV8058_101, CVN058 was well tolerated up to a dose of 150 mg administered orally as a single dose in aqueous solution. There were no deaths or other serious adverse events (SAEs) reported in this study and no subject discontinued study due to a treatment-emergent adverse event (TEAE). There were no clinically significant laboratory abnormalities, electrocardiogram (ECG) changes or changes in vital signs in the completed single dose study.

The mean C_{max} and area under the plasma concentration–time curve (AUC) values of CVN058 increased less than proportionally with increasing CVN058 dose across the dose range of 5 to 150 mg, but mean C_{max} and AUC values increased in an approximately dose proportional manner across the 5 to 45 mg dose range. The rate of appearance of CVN058 in plasma was rapid with median time to C_{max} (t_{max}) values of 1 to 1.25 hours across the dose range of 5 to 150 mg. The mean terminal elimination half-life ($t_{1/2z}$) values of CVN058 ranged from approximately 2.8 to 10.5 hours across the cohorts; the lower doses (5 to 30 mg) had lower mean $t_{1/2z}$ values compared to the higher doses (45 to 150 mg). There were no trends with mean apparent clearance values of CVN058 with increasing dose from 5 to 45 mg, but faster apparent clearance was observed at the 75 and 150 mg doses, possibly due to decreased bioavailability (BA) at higher doses. The mean apparent volume of distribution (Vz/F) increased as dose increased. Excretion of unchanged CVN058 in the urine was $\leq 2.3\%$ of the administered CVN058 dose over the dose range evaluated.

In the multiple-rising dose study (TAK-058-1002), CVN058 was well-tolerated at daily doses of 25, 75, and 150 mg for 7 days, and at a single 300 mg dose, in aqueous solution. There were no deaths or other SAEs reported in this study and no subject discontinued study due to a TEAE. There were no clinically significant laboratory abnormalities, ECG changes or changes in vital signs in the completed single dose study. Following single or multiple doses, the mean C_{max} and

AUC values of CVN058 increased less than proportionally with increasing CVN058 dose across the dose range of 25 to 300 mg. No accumulation was observed following daily administration. CVN058 concentrations in cerebrospinal fluid (CSF) were assessed after daily doses of CVN058 75 mg for 5 days. The CSF concentrations averaged 17.5 ng/mL, or approximately 1% of the concentration in plasma.

The statistical methods to be implemented during the analyses of data collected within the scope of the present study, CVN058-103, will be outlined in this document. The purpose of this plan is to provide specific guidelines from which the statistical analysis will proceed. Any deviations from this plan will be documented in the clinical study report.

2.3. Study Rationale

This study will explore central target engagement and proof of mechanism by measuring auditory evoked potential MMN as a pharmacodynamic (PD) marker of CNS response to the selective 5-HT3 receptor antagonist CVN058. It has been reported that subjects with schizophrenia commonly demonstrate a deficit in neural processing that is manifested as a reduction in MMN and impairment of auditory sensory gating (P50) [8]. Other 5-HT3 receptor antagonists have been reported to improve impairments in auditory evoked potentials in schizophrenic subjects. In a study with ondansetron, a widely-prescribed 5-HT3 receptor antagonist, using P50 auditory gating as the auditory evoked potential measure, subjects were given a single dose of ondansetron (16 mg) or placebo in a double-blind, placebo-controlled, randomized and balanced crossover design [9]. Serial measurements of the P50 evoked potential were done at Baseline and 1, 2, and 3 hours after receipt of placebo or ondansetron. The results of the study indicated that ondansetron significantly enhanced P50 auditory gating in subjects with schizophrenia. Tropisetron, a 5-HT3 antagonist that also has α 7 nicotinic cholinergic agonist activity, has similarly been shown to improve P50 auditory gating in subjects with schizophrenia [10].

While the P50 signal is likely a reflection of brainstem and thalamic network activity and is sensitive to antipsychotic treatment, MMN is thought to reflect excitation-inhibition balance in cortical circuits and is not sensitive to antipsychotic treatment [8]. Therefore, to evaluate the potential for CVN058 to improve cognitive function in schizophrenics, MMN will be used as a PD marker. The study will be performed as a 3-way crossover to assess the effect on MMN of CVN058 at two dose levels relative to placebo, with each subject serving as his or her own control to reduce variability. P50 auditory gating will also be measured, as an exploratory endpoint, along with other potentially informative electrophysiological and psychometric parameters.

Medications that might inhibit or mask the effects of CVN058 will not be permitted as concomitant medications. These include serotonin reuptake inhibitors which increase synaptic serotonin levels, as well as drugs that bind to 5-HT3 at clinically relevant concentrations or are reported to inhibit signaling through 5-HT3 non-competitively, including some antipsychotic drugs [11], [12], [13]. Permissible antipsychotic medications are risperidone (Risperdal), haloperidol (Haldol), quetiapine (Seroquel), aripiprazole (Abilify) and paliperidone (Invega).

3. Study Objectives and Endpoints

3.1. Objectives

3.1.1. Primary Objective

- To determine whether improvement in MMN is demonstrated after administration of CVN058 compared to placebo in subjects with schizophrenia.

3.1.2. Secondary Objective

- To assess the safety and tolerability of single doses of CVN058 in subjects with schizophrenia.

3.1.3. Exploratory Objectives

- To determine whether improvement in P50 auditory gating, gamma power, and P300 is demonstrated after administration of CVN058 compared to placebo in subjects with schizophrenia.

- [REDACTED]
- To explore the exposure-response relationship for CVN058 in subjects with schizophrenia.

3.2. Endpoints

[figure not shown]
3.2.1. Primary Endpoint (PDC Population)

- Mean amplitude of duration MMN at 5 electrodes surrounding frontal (Fz) electrodes following administration of CVN058 compared to placebo.

[figure not shown]
3.2.2. Secondary Endpoints (SAF Population)

- Percentage of subjects who experience at least one (1) TEAE
- Percentage of subjects who experience at least one (1) clinically significant abnormal laboratory test result

3.2.3. Exploratory Endpoints (PDC Population)

- Pre-stimulus gamma amplitude following administration of CVN058 compared to placebo
- P300 amplitude and latency at average of 5 centroparietal electrodes around parietal electrodes (Pz) following administration of CVN058 compared to placebo
- MMN amplitude to additional deviants (frequency, intensity, location, frequency-modulation) and latency to all deviants following administration of CVN058 compared to placebo

4. Study Design

4.1. Overall Study Design

This is a phase 1, double-blind, placebo-controlled, 3 period cross-over study to evaluate CVN058 target engagement by measuring auditory evoked potential MMN downstream to 5-HT3 as a pharmacodynamic (PD) marker.

4.2. Subjects

The study population will include male and female subjects with schizophrenia, age 18 to 50 years old, inclusive, and who satisfy all entry criteria.

4.3. Study Design Summary

In the initial study design, subjects were randomized to 1 of 6 treatment sequences to receive 1 of 3 dose regimens in each period. Each dose regimen consisted of a single oral administration of CVN058 (15 mg or 150 mg initially) or a matching placebo; study drug to be administered with water in the morning. The sequence will determine the order in which a subject will receive each of the 3 regimens. Discontinued subjects may be replaced so that 20 completed subjects are available for analysis.

After the Interim Analysis, the 15 mg dose in each treatment sequence was replaced with a 75 mg dose under Protocol Amendment 4, applicable to all subjects randomized.

Each treatment period is less than 1 day in duration, with a minimum of 7-day washout, maximum 10-day washout between doses. A follow-up telephone call will occur approximately 7-10 days following the last dose received. Subjects may be inpatients or outpatients at the discretion of the Investigator.

At each testing session, subjects will undergo post dose EEG testing including: MMN, P50, qEEG, gamma power, and P300. Testing sessions will begin approximately 1.5 hours post-dose. Prior to dose and at various time points post-dose, blood samples will be collected for the assessment of plasma concentrations of CVN058 and biomarkers.

Study procedures will be conducted at approximately the same times across Treatment Periods to minimize diurnal effects on outcomes. The effect of CVN058 on MMN as well as on exploratory measures (e.g., P50 auditory gating, gamma power, and P300) will be compared to placebo.

5. Determination of Sample Size

Enrollment of at least 20 subjects with schizophrenia (including schizoaffective disorder) is estimated to provide >80% power to detect a median effect size of Cohen's $d=0.5$. Discontinued or withdrawn subjects and subjects for whom MMN is not available for all three study periods may be replaced. The sample size chosen of at least 20 completed subjects is considered to be sufficient to explore the changes in MMN between CVN058 and placebo as well as safety and tolerability of CVN058 in this population. There will be approximately three (3) study sites in the United States. The sample size is subject to re-estimation based on preliminary data.

The sample size re-estimation will occur after twelve (12) subjects have completed all study visits. Full details are discussed in [Section 8](#).

6. Analysis Populations

Three subject populations will be defined for this study.

- Safety Set population (SAF): The Safety Set population will consist of all subjects who are randomized and receive study drug. Subjects in this analysis set will be used for demographic, baseline characteristics and safety summaries.
- Pharmacokinetic population (PK): The PK population will consist of all subjects who receive study drug and have at least one (1) measurable plasma concentration of CVN058.
- Pharmacodynamic population (PD): The PD population will consist of all subjects who receive study drug and have measurements in both the placebo-dosed period and at least one (1) CVN058-dosed period for at least one (1) EEG/evoked response endpoint.
- Pharmacodynamic completers population (PDC): The PDC population will consist of all subjects who receive study drug and have values in the placebo-dosed period and both CVN058-dosed periods for at least one (1) EEG/evoked response endpoint.

If any subjects are found to be noncompliant in dosing schedule or with incomplete data, a decision will be made on a case-by-case basis as to their inclusion in the PK and PD endpoint analyses, but data for all subjects will be presented in the subject listings.

7. Statistical Analysis

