7.1.4.1 Primary Analysis

The Primary Endpoint analysis will be performed on the PD population and will consist of a comparison of the post dose PD parameter Mean Amplitude of Duration MMN versus the parameter at time-matched placebo period timepoints using Generalized Linear Models with factors for sequence, subject nested within sequence, period, site and treatment. Two-sided 80% confidence intervals will be constructed for the least squares mean differences between CVN058 and placebo in PD parameters at the post-dose time point for each treatment period.

To maintain overall control of alpha (Type I error rate), the Primary Analysis will employ sequential testing, beginning with the higher dose (e.g., CVN058 150 mg) vs. Placebo using alpha = 0.10 and one-sided significance testing. If significant results are obtained from that first comparison, sequential significance testing of the next lower dose or doses (e.g., CVN058 75 mg) vs. Placebo will then be performed. If the first comparison yields a non-significant result, testing of the latter vs. Placebo will be performed to generate a nominal p-value, but that result will not be formally statistically significant regardless of the p-value.

Effect size will be calculated and summarized for comparisons of CVN058 to Placebo using Cohen's d which expresses the difference between the means of two groups as a function of their pooled standard deviation.

Exposure-response relationships for CVN058 will be explored graphically.

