8.1. Sample-size Re-assessment

Sample size re-estimation may occur when MMN data from all 3 periods are available for 12 patients, or when 20 patients have been dosed and are expected to complete the study, whichever is sooner. To ensure adequate study power, sample size may be increased up to a total of 40 patients.

The original study SAP describes procedures for a blinded interim analysis and sample size re-assessment. Upon review of the outputs from the blinded interim analysis (which included data only from the first 12 subjects, who had already completed the study), the Sponsor determined that an unblinded analysis of those interim data is necessary to properly inform decisions about study continuation and dose selection. Unblinding of the interim analysis data was thus introduced in Protocol Amendment 4, and the SAP has been modified accordingly.

The unblinded sample size re-estimation procedure will be performed utilizing the following steps:

- 1) Based on treatment allocations, only subjects with evaluable MMN data from all three study periods will be included in the sample size re-estimation.
- 2) Sample size re-estimation calculation will be based on the specifications of approximately 80% power and alpha=0.10 utilizing SAS Proc GLMPOWER for Analysis of Variance and the unblinded group values by treatment assignment (placebo, CVN058 15 mg, CVN058 150 mg) and standard deviation values from the twelve (12) study subjects.

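### The stated >80% power at 20 subjects fits 150 mg versus placebo but not 75 mg versus placebo, for which at most 8 of the 20 would have a 75 mg period

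*SAP*

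**What the plan says.** Section 5 makes a single power statement: "Enrollment of at least 20 subjects with schizophrenia (including schizoaffective disorder) is estimated to provide >80% power to detect" an effect of Cohen's d=0.5. It does not say which dose is meant or which standard deviation scales d. It describes 20 as a minimum that is open to re-estimation.

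Section 4.3 records the dose change: "After the Interim Analysis, the 15 mg dose in each treatment sequence was replaced with a 75 mg dose under Protocol Amendment 4".

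Section 7.1.4.1 sets a fixed testing order at one-sided alpha 0.10. The first test is 150 mg against placebo. If that is significant, "sequential significance testing of the next lower dose or doses (e.g., CVN058 75 mg) vs. Placebo will then be performed". The same section plans interval estimates ("Two-sided 80% confidence intervals will be constructed for the least squares mean differences between CVN058 and placebo") and defines Cohen's d as a measure "which expresses the difference between the means of two groups as a function of their pooled standard deviation".

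Section 8.1 describes the interim data as outputs "which included data only from the first 12 subjects, who had already completed the study". It bases the unblinded re-estimation on "the unblinded group values by treatment assignment (placebo, CVN058 15 mg, CVN058 150 mg") and their standard deviations. It also says that "sample size may be increased up to a total of 40 patients".

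**The concern.** The first 12 subjects finished the study before 75 mg was introduced. They contribute directly to the 150 mg comparison but have no 75 mg period, so the number of subjects with a 75 mg period is at most N−12. Section 5 still reads as though one figure covers CVN058 against placebo at either dose.

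The 75 mg test is the second step of the alpha-controlled primary sequence, and that dose was introduced after the interim analysis, so its result bears on dose selection. If the final N is at or near 20, a non-significant 75 mg result would be read against a stated chance of missing a true d=0.5 effect of under 20%. At r=0.5 the actual chance would be about 41–48%.

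**Working it through.** **Inputs from the SAP.** N=20, power >80%, d=0.5 (Section 5); one-sided alpha 0.10, and a model with sequence, subject within sequence, period, site and treatment (7.1.4.1); 12 completers on placebo, 15 mg and 150 mg (8.1); maximum N of 40 (8.1).

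**Assumptions.** d=0.5 is on the pooled SD, the only definition the SAP gives. The between-period correlation r is not given, so a range is shown. The standardised within-subject difference is d_z = 0.5/√(2(1−r)). At r=0.5 this is 0.5, so that row also covers the reading in which d is scaled by the SD of the within-subject difference.

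**Step 1: reproduce the stated figure.** Use a paired t-test with noncentrality d_z·√n.
- n=20, r=0.5: noncentrality 0.5 × √20 = 2.236, critical t (19 df) 1.328, power 81.7%. This matches >80%.
- At n=20, power reaches 80% at r of about 0.47, so the stated figure needs r at or above that.

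**Step 2: the same test for 75 mg at N=20.** Subjects with a 75 mg period: 20 − 12 = 8.
- n=8, r=0.5: noncentrality 0.5 × √8 = 1.414, critical t (7 df) 1.415, power 51.9%.

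**Step 3: the planned model.** It has fixed effects for subject, period and treatment (placebo, 15, 75, 150 mg); subject absorbs sequence and site. Twelve subjects receive placebo/15/150 and eight receive placebo/75/150, with sequences as balanced as possible and no missing periods. This model also uses indirect information on 75 mg that comes through the 150 mg periods.
- Residual df: 60 − 20 − 2 − 3 = 35.
- Variance of 75 mg minus placebo: 0.2148 σ_w². Variance of 150 mg minus placebo: 0.1008 σ_w².
- Standard error ratio: √(0.2148/0.1008) = 1.46. This does not depend on the effect size or on r.
- Effective number of pairs for 75 mg: 2/0.2148 = 9.3.
- Noncentrality is d_z·√(2/variance factor). At r=0.5, power is 58.9% for 75 mg and 82.1% for 150 mg.
- Half-width of the 80% interval, in SDs of the within-subject difference, with t(0.90, 35 df) = 1.306: 1.306 × √(0.2148/2) = 0.43 for 75 mg and 1.306 × √(0.1008/2) = 0.29 for 150 mg.

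**Step 4: vary r at N=20.**

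| r | d_z | 75 mg, paired t (n=8) | 75 mg, model | 150 mg, model |
|---|---|---|---|---|
| 0.5 | 0.500 | 52% | 59% | 82% |
| 0.6 | 0.559 | 58% | 66% | 88% |
| 0.7 | 0.645 | 67% | 75% | 94% |
| 0.8 | 0.791 | 79% | 86% | 99% |

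Power for 75 mg reaches 80% at r of about 0.75 under the model and just above 0.80 by paired t.

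**Step 5: vary the final N (75 mg power, paired t to model).**

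| N | Subjects with 75 mg | r=0.5 | r=0.7 |
|---|---|---|---|
| 20 | 8 | 52–59% | 67–75% |
| 24 | 12 | 65–71% | 81–86% |
| 28 | 16 | 75–79% | 89–92% |
| 40 | 28 | 91–93% | 98–99% |

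Twenty subjects with a 75 mg period require N=32, where power at r=0.5 is 82% (paired t) to 85% (model). The standard error ratio falls to 1.15 at N=40.

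**The case against.** The strongest reply is that 20 is not offered as the final size. Section 5 says at least 20, subject to re-estimation; Section 8.1 allows 40; and Section 8.2 adds conditional-power calculations up to 40 before any stop for futility. At r=0.5 the planned model already gives 82.6% for 75 mg at N=30. That stands, and it makes the shortfall conditional on the final N. It does not remove it: the increase is optional, and the calculation in 8.1 uses placebo, 15 mg and 150 mg values only, so no 75 mg requirement enters it.

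Second, the SAP gives no r, and at a high enough r the 75 mg test does reach 80% with N=20. This also stands. It needs r of roughly 0.75 or more, where 150 mg would have about 97% power, well above the floor Section 5 states.

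Third, the 52% comes from a paired test that the SAP does not plan. The model figure of 59% is the closer one, and both are shown for that reason.

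Fourth, sizing a fixed sequence on its first test is ordinary practice, Section 5 never attributes its figure to 75 mg, and this is a phase 1 mechanism study. That is a fair defence of the sample size. It does not defend a power statement that names no dose when the two primary comparisons differ this much in precision.

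Last, not naming the SD behind d would by itself be only a missing detail. The conclusion does not depend on it.

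**Conclusion.** The concern holds. As written, the >80% at 20 subjects is right for 150 mg versus placebo if r is about 0.47 or more. It is not right for 75 mg versus placebo unless r is about 0.75 (model) to 0.80 (paired t) or higher. At N=20 and r=0.5, power for 75 mg is 52–59% against 82% for 150 mg, and the 75 mg standard error is 1.46 times as large at any r.

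This rests on one-sided alpha 0.10, d=0.5 on the pooled SD, the first 12 subjects staying in the final analysis, balanced sequences and no missing periods. N−12 is an upper limit: if more than 12 subjects received 15 mg, 75 mg power is lower. Because 75 mg is formally tested only after 150 mg succeeds, the chance of a formal 75 mg success is at most these figures. The shortfall shrinks as N rises and has largely gone by N=40. The point should be corrected, but it does not threaten the 150 mg comparison.

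**What to change.** In Section 5:
- State power separately for each dose, with the SD that scales d and the correlation assumed.
- Say that >80% at N=20 applies to 150 mg versus placebo only.
- Give 75 mg power as a function of the number of completers with a 75 mg period (N minus at least 12). If the sponsor adopts r=0.5, that is 52–59% at N=20 and 91–93% at N=40; under another r, use the matching figures.
- Add that at N=20 the 75 mg comparison does not have the stated power, so a non-significant 75 mg result will be interpreted from its planned 80% confidence interval.

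The cost is a few sentences. Enrolment, model, test order and alpha stay as they are.
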